3.5.2. Laboratory Data

Safety laboratory tests will be performed as described in the protocol. Baseline is defined as the last pre-dose measurement collected on Day -1.

To determine if there are any clinically significant laboratory abnormalities, the hematology, chemistry, and urinalysis tests will be assessed against the criteria specified in Clinical Data Interchange Standards Consortium (CDISC) standard. The assessment will not take into account whether each participant's baseline test result is within or outside the laboratory reference range for the particular laboratory parameter.

3.5.3. Vital Signs Data

Supine blood pressure (BP) and pulse rate (PR) will be taken at times detailed in the SoA given in the protocol. The measurements collected prior to dosing on Day 1 will serve as baseline. Change from baseline in supine BP and PR will be determined.

3.5.4. ECG Data

Standard 12-lead electrocardiograms (ECG) will be obtained at each assessment time indicated in the SoA given in the protocol. Baseline will be defined as the last pre-dose recordings on Day 1. Change from baseline in QT interval, heart rate, QTcF interval, PR interval, and QRS interval will be determined.

4. ANALYSIS SETS (POPULATIONS FOR ANALYSIS)

For purposes of analysis, the following analysis sets are defined:

Participant Analysis Set	Description	Applicable Analysis (for additional information refer to section 6)
Enrolled	"Enrolled" means a participant's, or their legally authorized representative's, agreement to participate in a clinical study following completion of the informed consent process and assignment to study intervention. A participant will be considered enrolled if the informed consent is not withdrawn prior to participating in any study activity. Potential participants who are screened for the purpose of determining eligibility for the study, but do not participate in the study, are not considered enrolled, unless otherwise specified by the protocol.	
PK Concentration Analysis Set	All enrolled participants who receive 1 single IN dose of zavegeptan and provide at least 1 evaluable plasma concentration.	Primary endpoints (section 6.1) and secondary endpoints (additional PK parameter, section 6.2)

Participant Analysis Set	Description	Applicable Analysis (for additional information refer to section 6)
PK Parameter Analysis Set	All enrolled participants who receive 1 single IN dose of zavegepant and provide at least 1 evaluable PK parameters of interest.	Primary endpoints (section 6.1) and secondary endpoints (additional PK parameter, section 6.2)
Safety Analysis Set	All enrolled participants who receive 1 single IN dose of zavegepant. Participants will be analyzed according to the product they actually received.	Secondary endpoints (safety endpoints, section 6.2)

5. GENERAL METHODOLOGY AND CONVENTIONS

5.1. Hypotheses and Decision Rules

There are no statistical hypotheses for this study.

5.2. General Methods

All data will be descriptively summarized.

Binary and categorical variables will be presented using summary statistics: number of observations and percentages.

Continuous variables will be presented using summary statistics: number of observations, arithmetic mean, standard deviation (SD), coefficient of variation (cv%), median, minimum, maximum, geometric mean and geometric cv%.

5.3. Methods to Manage Missing Data

5.3.1. Safety Data

For the analysis of safety endpoints, the sponsor data standard rules for imputation will be applied.

5.3.2. Pharmacokinetic Data

Concentrations Below the Limit of Quantification

In all PK data presentations (except listings), concentrations below the limit of quantification (BLQ) will be set to zero.

In listings, BLQ values will be reported as “<LLQ”, where LLQ will be replaced with the value for the lower limit of quantification (LLQ).

Deviations, Missing Concentrations and Anomalous Values

For PK summary tables, plots of mean profiles and plots of median profiles, summary statistics will be calculated setting concentrations to missing if one of the following cases is true:

1. A concentration has been collected as ND (i.e., not done) or NS (i.e., no sample);
2. A deviation in sampling time is of sufficient concern or a concentration has been flagged anomalous by the pharmacokineticist.

Note that summary statistics will not be presented at a particular time point if more than 50% of the data are missing.

Pharmacokinetic Parameters

Actual PK sampling times will be used in the derivation of PK parameters.

If a PK parameter cannot be derived from a participant's concentration data, the parameter will be coded as NC (i.e., not calculated). (Note that NC values will not be generated beyond the day that a participant discontinues.)

In summary tables, statistics will be calculated by setting NC values to missing; and statistics will not be presented if more than 50% of the data are NC.

If an individual participant has a known biased estimate of a PK parameter (e.g., due to an unexpected event such as vomiting before all the compound is adequately absorbed in the body), this will be footnoted in summary tables and will not be included in the calculation of summary statistics. For PK parameter calculations, the sponsor standard rules will be applied.

6. ANALYSES AND SUMMARIES

6.1. Primary Endpoint(s)

The zavegepant plasma PK parameters detailed in [Section 3.1](#) will be listed and descriptively summarized based on the PK parameter analysis set (as defined in [Section 4](#)). Missing values will be handled as detailed in [Section 5.3.2](#). Each summary will include the set of summary statistics as specified in Table 3.

Table 3. PK Parameters to be Summarized Descriptively

Parameter	Summary Statistics
C_{max} , AUC_{last} , AUC_{inf} , CL/F , and V_z/F	N, arithmetic mean, median, $cv\%$, SD, minimum, maximum, geometric mean and geometric $cv\%$.
T_{max}	N, median, minimum, maximum.
$t_{1/2}$	N, arithmetic mean, median, SD, minimum, maximum.

For C_{\max} , AUC_{last} , and AUC_{inf} , box and whisker plots for individual participant parameters overlaid with geometric means will be plotted. Supporting data from the estimation of $t_{1/2}$ will be listed where applicable.

The plasma zavegepant concentrations will be presented within the PK concentration analysis set (as defined in Section 4) and will include:

- a listing of all concentrations sorted by participant ID, study day, and nominal time post-dose. The concentration listing will also include the actual times. Deviations from the nominal time will be given in a separate listing.
- a summary of concentrations by study day, and nominal time post-dose, where the set of statistics will include number of observations, mean, median, SD, cv%, minimum, maximum and the number of concentrations above the LLQ.
- median concentration-time plots (on both linear and semi-log scales) against nominal time post-dose.
- mean concentration-time plots (on both linear and semi-log scales) against nominal time post-dose.
- individual concentration-time plots (on both linear and semi-log scales) against actual time post-dose.

The scale used for the x-axis (time) of these plots will be decided on review of the data, and will depend on how long zavegepant concentrations are quantifiable.

For summary statistics, median and mean plots by sampling time, the nominal PK sampling time will be used, for individual plots by time, the actual PK sampling time will be used. For pre-dose, the actual PK sampling time will be set to 0 hour.

6.2. Secondary Endpoint(s)

The details of safety analyses are described in Section 6.5.

The additional zavegepant plasma PK parameters detailed in Section 3.2 will be summarized and plotted the same as the primary endpoints described in Section 6.1.

6.3. Subset Analyses

No subset analyses will be performed.

6.4. Baseline and Other Summaries and Analyses

6.4.1. Baseline Summaries

Demographic and baseline characteristics collected prior to the first dosing will be summarized following CDISC standard.

6.4.2. Study Conduct and Participant Disposition

A participant disposition table will be provided. Participant disposition will be summarized and will include the number and percentage of participants randomized, treated, completing and discontinuing from the study, the number of participants in each analysis population and reasons for discontinuation of study. The percentages will use the number of randomized as the denominator.

6.4.3. Concomitant Medications and Nondrug Treatments

All concomitant medication(s) as well as non-drug treatment(s) will be reported according to CDISC standard.

6.5. Safety Summaries and Analyses

Standard summary tables and listings will be generated in accordance with CDISC standard within safety analysis set (as defined in Section 4).

6.5.1. Adverse Events

All AEs will be coded according to the Medical Dictionary for Regulatory Activities (MedDRA) and will be listed and summarized.

6.5.2. Laboratory Data

Laboratory data will be listed and summarized. Baseline is as defined in Section 3.5.2.

Incidence of laboratory test (including hematological, clinical chemistry and urine test) abnormalities (without regard to baseline abnormality) will be reported.

6.5.3. Vital Signs

BP and PR will be summarized using Pfizer's implementation of CDISC standards. For each planned timepoint, absolute values and change from baseline values will be summarized with descriptive statistics. Baseline is as defined in Section 3.5.3.

Minimum and/or maximum absolute values and changes from baseline for vital signs will also be summarized descriptively using categories as defined below. Numbers and percentages of participants meeting the categorical criteria will be provided.

Categories for Vital Signs Endpoints

Systolic BP (mm Hg)	min. <90	
Systolic BP (mm Hg) change from baseline	max. decrease ≥ 30	max. increase ≥ 30
Diastolic BP (mm Hg)	min. <50	
Diastolic BP (mm Hg) change from baseline	max. decrease ≥ 20	max. increase ≥ 20
Pulse rate (bpm)	min. <40	max. >120

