 - Biologic CGRP receptor antagonist within 6 months prior to dosing;
 - Oxymetazoline (or other nasal spray decongestants) from at least 14 days prior to the first dosing;
 - Receipt of any vaccination, including COVID-19 vaccine, within 14 days prior to first dosing.

Prior/Concurrent Clinical Study Experience:

7. Participation in a clinical research study involving the administration of an investigational or marketed drug or device within 30 days prior to the first dosing, administration of a biological product in the context of a clinical research study within 90 days prior to the first dosing, or concomitant participation in an investigational study involving no drug or device administration.

Diagnostic Assessments:

8. Any clinically significant abnormal laboratory test results or positive test found during medical screening.
9. Evidence of organ dysfunction or any clinically significant deviation from normal in physical examination, nasal inspection, vital signs, 12-lead ECG, or clinical laboratory determinations beyond what is consistent with the target population.

10. Screening supine BP ≥ 140 mm Hg (systolic) or ≥ 90 mm Hg (diastolic), following at least 5 minutes of supine rest. If BP is ≥ 140 mm Hg (systolic) or ≥ 90 mm Hg (diastolic), the BP should be repeated 2 more times and the average of the 3 BP values should be used to determine the participant's eligibility.
11. Standard 12-lead ECG that demonstrates clinically relevant abnormalities that may affect participant safety or interpretation of study results (eg, QTcF > 450 ms, complete LBBB, signs of an acute or indeterminate- age myocardial infarction, ST-T interval changes suggestive of myocardial ischemia, second- or third- degree AV block, or serious bradyarrhythmias or tachyarrhythmias). If the uncorrected QT interval is > 450 ms, this interval should be rate-corrected using the Fridericia method only and the resulting QTcF should be used for decision making and reporting. If QTcF exceeds 450 ms, or QRS exceeds 120 ms, the ECG should be repeated twice and the average of the 3 QTcF or QRS values used to determine the participant's eligibility. Computer-interpreted ECGs should be overread by a physician experienced in reading ECGs before excluding a participant.
12. Participants with **ANY** of the following abnormalities in clinical laboratory tests at screening, as assessed by the study-specific laboratory and confirmed by a single repeat test, if deemed necessary:

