8.3.3. Vital Signs

8.3.3.1. Blood Pressure and Pulse Rate

Supine BP will be measured with the participant's arm supported at the level of the heart, and recorded to the nearest mm Hg after approximately 5 minutes of rest. The same arm (preferably the dominant arm) will be used throughout the study. Participants should be instructed not to speak during measurements.

The same properly sized and calibrated BP cuff will be used to measure BP each time. The use of an automated device for measuring BP and pulse rate is acceptable; however, when done manually, pulse rate will be measured in the brachial/radial artery for at least 30 seconds. When the timing of these measurements coincides with a blood collection, BP and pulse rate should be obtained prior to the nominal time of the blood collection.

Additional collection times, or changes to collection times, of BP and pulse rate will be permitted, as necessary, to ensure appropriate collection of safety data.

Any untoward vital sign findings that are identified during the active collection period and meet the definition of an AE or SAE ([Appendix 3](#)) must be reported according to the processes in [Sections 8.4.1 to 8.4.3](#).

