9.3.3. Safety Analyses

All safety analyses will be performed on the safety population.

AEs, ECGs, BP, pulse rate, and safety laboratory data will be reviewed and summarized on an ongoing basis during the study to evaluate the safety of participants. Any clinical laboratory, ECG, BP, and pulse rate abnormalities of potential clinical concern will be described. Safety data will be presented in tabular and/or graphical format and summarized descriptively, where appropriate.

Medical history and physical examination collected during the course of the study, will be considered source data and will not be required to be reported, unless otherwise noted. However, any untoward findings identified on physical examinations conducted during the active collection period will be captured as AEs, if those findings meet the definition of an AE. Data collected at screening that are used for inclusion/exclusion criteria, such as laboratory data, ECGs, and vital signs, will be considered source data, and will not be required to be reported, unless otherwise noted. Demographic data collected at screening will be reported.

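### SAP 6.5.3 has no upper absolute category for blood pressure, so a new high reading such as 159/99 from a baseline of 130/80 is counted in no BP category

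*SAP*

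**What the plan says.** SAP 6.5.3 plans two displays for BP and pulse rate. The first is descriptive statistics of values and changes at each planned timepoint. The second is a categorical count, introduced as follows: "Minimum and/or maximum absolute values and changes from baseline for vital signs will also be summarized descriptively using categories as defined below". Each category is to be reported as a participant count with its percentage.

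The BP rows of the category table are:

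- systolic, absolute: minimum below 90, with no upper entry
- systolic, change: a fall of 30 or more, or "max. increase ≥ 30"
- diastolic, absolute: minimum below 50, with no upper entry
- diastolic, change: a fall of 20 or more, or "max. increase ≥ 20"

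On baseline, SAP 3.5.3 says: "The measurements collected prior to dosing on Day 1 will serve as baseline". Protocol 9.3.3 commits that "Any clinical laboratory, ECG, BP, and pulse rate abnormalities of potential clinical concern will be described", without giving a BP level. The one high-side BP level in the protocol is exclusion criterion 10 in section 5.2: "Screening supine BP ≥ 140 mm Hg (systolic) or ≥ 90 mm Hg (diastolic), following at least 5 minutes of supine rest".

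**The concern.** Vital signs are a named secondary safety endpoint, and the category table is where the SAP turns them into participant counts. Low BP can enter that table by level or by change. High BP can enter only by change. A participant who starts in the upper part of the normal range and ends clearly above 140/90 may rise by less than 30/20 and so be counted nowhere.

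Neither document defines a high post-dose BP level elsewhere. Protocol Appendix 6 lists findings of potential clinical concern for ECG only. The commitment in Protocol 9.3.3 to describe BP abnormalities therefore has no stated high-side level behind it. At stake is whether the categorical safety summary is complete. No estimate, test or decision rule is affected.

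**Working it through.** The plan states no figure to reproduce. The check applies the six BP rules to whole-number readings and finds the highest reading that meets none of them.

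**Inputs**

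- Increase limits: 30 systolic and 20 diastolic (SAP 6.5.3).
- Absolute limits: below 90 systolic and below 50 diastolic, low side only (SAP 6.5.3).
- Precision: BP is "recorded to the nearest mm Hg after approximately 5 minutes of rest" (Protocol 8.3.3.1), so the largest uncounted rise is 29 systolic and 19 diastolic.
- Baseline: the Day 1 pre-dose reading (SAP 3.5.3).
- Reference level for calling a reading high: 140/90, borrowed from criterion 10.

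**Formulas**

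Highest uncounted systolic = baseline + 29. Highest uncounted diastolic = baseline + 19.

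| Day 1 baseline | Highest uncounted reading | Uncounted readings at or above 140 / 90 |
|---|---|---|
| 110/70 | 110+29 = 139 / 70+19 = 89 | none / none |
| 120/75 | 120+29 = 149 / 75+19 = 94 | 140–149 / 90–94 |
| 130/80 | 130+29 = 159 / 80+19 = 99 | 140–159 / 90–99 |

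**Check of the 130/80 row.** At 159/99, systolic is not below 90, diastolic is not below 50, there is no fall, and the rises are 29 and 19. No category is met. At 160/100 the rises are 30 and 20, and both increase categories are met.

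**Where the gap opens.** A new reading of 140 escapes once baseline systolic exceeds 110 (111 + 29 = 140). A new reading of 90 escapes once baseline diastolic exceeds 70 (71 + 19 = 90). At or below 110/70 the change rows already catch every reading of 140/90 or more.

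**Comparison with the other parameters given numeric categories (SAP 6.5.3 and 6.5.4)**

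| Parameter | Absolute lower | Absolute upper | Change |
|---|---|---|---|
| Systolic BP | <90 | none | fall or rise ≥30 |
| Diastolic BP | <50 | none | fall or rise ≥20 |
| Pulse rate | <40 | >120 | none |
| QTcF | none | bands from >450 | increase bands |
| PR | none | ≥300 | increase ≥25% or ≥50%, by baseline |
| QRS | none | ≥140 | increase ≥50% |

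Only the two BP parameters lack an absolute upper limit. The SAP gives no reason.

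**The case against.** The case for leaving the table alone is reasonable in several respects.

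- **The SAP does not contradict itself.** The lead-in allows minimum and/or maximum, and the ECG table also leaves positions empty. High BP is represented through the increase rows. This stands: the point concerns completeness and is not an error of logic.
- **The reading stays visible.** The by-timepoint summary includes the maximum (SAP 5.2). SAP 6.5 plans listings, with about 12 participants to read through. Vital-sign findings that meet the AE definition must be reported as AEs. If every baseline is below 140/90, a post-dose maximum at or above that level must be new. All this stands, but none of it gives the number of participants with a new high reading, and AE reporting depends on the investigator's judgement.
- **Other flags may exist.** SAP 6.5.3 refers to the sponsor's implementation of CDISC standards, whose content is not in the documents. This cannot be excluded, but the SAP's own table is the stated prespecification.
- **140/90 is a screening rule.** For a high value at screening, "the BP should be repeated 2 more times and the average of the 3 BP values should be used to determine the participant's eligibility". A single post-dose reading is not equivalent. This stands, and it limits the level to a descriptive reporting cut-off.

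Two stronger readings are tempting. A reader might take 139/89, the highest eligible screening value, add 29/19, and conclude that 168/108 is the largest reading that can escape. It is neither typical nor a bound. It needs a baseline at the eligibility edge; from 120/75 the same reading is counted as both a systolic and a diastolic increase. The exclusion applies at screening while baseline is Day 1 pre-dose, so an assumed higher Day 1 value of 145/92 would move the figure to 174/111. A reader might also infer that the table would report zero participants with high BP. It has no such row, and a zero in the increase row would be correct for what that row counts.

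**Conclusion.** The point holds as a minor, cheap improvement. Followed as written, the categorical table can show that no participant met any BP criterion although one or more had a new reading above 140/90. The size of the blind range depends on baseline: up to 149/94 from 120/75, and up to 159/99 from 130/80.

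This rests on whole-number recording, on the table as printed, and on 140/90 as a reference level, which is a choice and not a post-dose criterion in the plan. The documents give no BP distribution for this population and no expected effect of the drug on BP, so they do not support a statement of how often such readings would occur. They also do not support saying that high readings go unreported: only the categorical count misses them.

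**What to change.** In the SAP 6.5.3 table, add an upper absolute category to each BP row, for example systolic maximum of 140 or more and diastolic maximum of 90 or more. These are the numeric limits of criterion 10, used only as descriptive reporting cut-offs on scheduled readings and not as a rule for managing participants. If the sponsor prefers other limits, prespecify and justify them.

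For each category, count participants who reach the limit at any scheduled post-dose reading and whose Day 1 pre-dose baseline was below it. Keep all existing rows.

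The cost is two table cells and a line of definition, using readings already scheduled. The downside is that some borderline single readings, such as a move from 138 to 141, will be counted, so the table may look slightly less favourable. A footnote that these are single unrepeated readings would keep that in proportion.

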6.5.4. Electrocardiograms

Absolute values and changes from baseline in QT interval, heart rate, QTcF interval, PR interval, and QRS complex will be summarized descriptively by time. Baseline is as defined in Section 3.5.4.

Maximum and/or minimum absolute values and changes from baseline for ECG endpoints (QTcF interval, PR interval and QRS complex) will also be summarized using categories as defined in below table. Numbers and percentages of participants meeting the categorical criteria will be provided.

Categories for ECG Endpoints

QTcF (msec)	450< max. \leq 480	480< max. \leq 500	max. $>$ 500
QTcF (msec) increase from baseline	30< max. \leq 60	max. $>$ 60	
PR (ms)	max. \geq 300		
PR (ms) increase from baseline	baseline $>$ 200 and max. \geq 25% increase	baseline \leq 200 and max. \geq 50% increase	
QRS (ms)	max. \geq 140		
QRS (ms) increase from baseline	\geq 50% increase		

6.5.5. Other Safety Data

Medical history and physical examination collected during the course of the study, will be considered source data and will not be required to be reported, unless otherwise noted. However, any untoward findings identified on physical examinations conducted during the active collection period will be captured as AEs, if those findings meet the definition of an AE.

